15.1. Adverse Events

Patients with multiple adverse events in the same category are counted only once in that category and those with adverse events in more than 1 category are counted once in each of those categories. Adverse Events (AEs) will be coded using Medical Dictionary for Regulatory Activities (MedDRA) central coding dictionary, using the latest version of MedDRA available at the time of coding for the reporting period.

Treatment-emergent adverse events (TEAEs) are defined as AEs that started or worsened in severity from the date of first dose of the rollover study (regardless of time) up until 90 days after the last dose of study drug of this rollover study.

See [APPENDIX 2](#) for handling of partial dates for AEs. In the case where it is not possible to define an AE as treatment-emergent or not, the AE will be classified by the worst case; i.e. treatment emergent.

An overall summary of number of patients within each of the categories described in the subsection below, will be provided as specified in the templates.

An AE Listing will include TEAEs and Non-TEAEs, including those from before the first dose in the parent study and post-treatment periods which will be flagged as such. Only TEAEs will be summarized.

AE Structure as Recorded in the eCRF:

AEs will be recorded in the eCRF such that any change in severity over the course of their duration will be recorded as a single record. The AE/SAE eCRF page collects ‘Initial Grade’ and ‘Most Extreme Grade’ but not the date of the severity grade change. No further manipulation post collection is required, and the AE/SAE data will be listed as recorded.

The definition of a treatment-emergent AE will be handled for AEs that change in severity over the course of their duration, by assuming that any AE that *might have worsened* in severity within the timeframe from the date of first dose of the rollover study (regardless of time) up until 90 days after the last dose of study drug, will be defined as treatment-emergent. A worsening severity is defined as changing from a less severe (lower) CTCAE grade to a more severe (higher) CTCAE grade. For example, if an AE started prior to date of first dose of the parent study but ended on or after date of first dose of the parent study (regardless of time), and the ‘Most Extreme Grade’ is more severe (higher) than the ‘Initial Grade’, then the AE is assumed to be treatment-emergent.

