## 8 ADVERSE EVENTS AND SAFETY REPORTING

### 8.1 Assessment of Safety

All patients who receive any treatment with IMCgp100 will be considered evaluable for safety. All AEs, regardless of study drug relationship, will be collected through the 90-day Safety Follow-up Period. At the time of consent, if any patient has any ongoing AE(s) from the parent IMCgp100 study, the AE(s) will be captured on the eCRF page and the "Ongoing at Start of Study" must be answered "Yes". The start date recorded in the eCRF for the rollover study should be equal to the start date of the event as recorded in the parent study. Timely, accurate, and complete reporting and analysis of safety information from clinical studies are crucial for the protection of patients and is mandated by regulatory agencies worldwide. The Sponsor and CRO have established standard operating procedures in conformity with regulatory requirements worldwide to ensure appropriate reporting of all safety information. All clinical studies conducted by the Sponsor or its affiliates will be conducted in accordance with those procedures.

Individual AEs should be evaluated by the investigator and should be reported to the CRO/Sponsor for evaluation. This includes the evaluation of the event's seriousness and the causality between the investigational medicinal product(s) and/or concomitant therapy and the AE. The CRO/Sponsor is required to maintain detailed records of all AEs reported by the investigator(s) and to perform an evaluation with respect to seriousness, causality, and expectedness. On request of a competent authority in whose territory the clinical trial is being conducted, the Sponsor should submit detailed records of all AEs which are reported by the relevant investigators. Case report processing concerns evaluation of data in individual cases, identification of individual cases requiring specific handling, recognition and processing of alerts, and any other data processing of aggregated cases.

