#### **9.6.1.1 Adverse Events**

Summary tables for AEs include only AEs that are new or worsened during the on-treatment period (treatment-emergent AEs). However, all safety data (including those from the pre- and post-treatment periods) will be listed and those collected during the pre-treatment and post-treatment period are to be flagged.

The incidence of treatment-emergent AEs will be summarized by system organ class and/or preferred term, severity (based on NCI CTCAE v.4.03 grades), type of AE, and relation to study treatment by treatment group. Deaths reportable as SAEs and non-fatal SAEs will be listed by patient and tabulated by type of AE and treatment group.

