## **9.9 Sample Size Calculation**

No formal sample sizing will apply to this study.

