2.1. Primary Objective

The primary objective is to determine the number of patients with adverse events (AEs) associated with IMCgp100 treatment.

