6.5. Statistical Tests

There will be no formal statistical hypotheses testing.

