APPENDIX 2. Partial Date Conventions

Imputed dates will NOT be presented in the listings.

ALGORITHM FOR TREATMENT EMERGENCE OF ADVERSE EVENTS:

START DATE	STOP DATE	ACTION
Known	Known	If start date < study drug start date, then not TEAE If start date ≥ study drug start date and start date ≤ study drug end date + 90, then TEAE If start date > study drug end date + 90, then not TEAE Note: If study drug end date is missing, then as long as start date ≥ study drug start date, then TEAE
	Partial	If start date < study drug start date, then not TEAE If start date ≥ study drug start date and start date ≤ study drug end date + 90, then TEAE If start date > study drug end date + 90, then not TEAE Note: If study drug end date is missing, then as long as start date ≥ study drug start date, then TEAE
	Missing	If start date < study drug start date, then not TEAE If start date ≥ study drug start date and start date ≤ study drug end date + 90, then TEAE If start date > study drug end date + 90, then not TEAE Note: If study drug end date is missing, then as long as start date ≥ study drug start date, then TEAE
Partial, but known	Known	Not TEAE

START DATE	STOP DATE	ACTION
components (month/year or year) show that start date cannot be on or after study drug start date		
	Partial	Not TEAE
	Missing	Not TEAE
Partial, could be on or after study drug start date (i.e. same month/year or after, or year after)	Known	
If stop date < study drug start date, then not TEAE
 
If stop date ≥ study drug start date, then impute start date as earliest possible date (i.e. first day of month if day unknown or 1st January if day and month are unknown). Then, consider the following:
 
 -If start date ≤ study drug end date + 90, then TEAE -If start date > study drug end date + 90, then not TEAE 
Note: If study drug end date is missing, then as long as the imputed start date ≥ study drug start date, then TEAE

	Partial	
Impute stop date as latest possible date (i.e. last day of month if day unknown or 31st December if day and month are unknown), then:
 
If stop date < study drug start date, then not TEAE
 
If stop date ≥ study drug start date, then impute start date as earliest possible date (i.e. first day of month if day unknown or 1st January if day and month are unknown). Then, consider the following:
 
 -If start date ≤ study drug end date + 90, then TEAE

START DATE	STOP DATE	ACTION

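### SAP 15.1 and Appendix 2 classify AEs carried over from the parent study by conflicting rules, and neither reliably identifies those that worsened on rollover treatment

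*SAP*

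**What the plan says.** The primary objective is a patient count: "The primary objective is to determine the number of patients with adverse events (AEs) associated with IMCgp100 treatment" (SAP 2.1). Protocol 9.6.1.1 sets the scope of the tables: "Summary tables for AEs include only AEs that are new or worsened during the on-treatment period". The definition in SAP 15.1 matches it: an AE is treatment-emergent if it starts or worsens between the first rollover dose and 90 days after the last.

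Protocol 8.1 covers AEs already present at consent: "if any patient has any ongoing AE(s) from the parent IMCgp100 study, the AE(s) will be captured on the eCRF page", with a flag that they were ongoing at study start. The start date entered "should be equal to the start date of the event as recorded in the parent study".

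SAP 15.1 keeps one record for the whole life of an AE. On grades it says: "The AE/SAE eCRF page collects ‘Initial Grade’ and ‘Most Extreme Grade’ but not the date of the severity grade change". Because the timing of a grade change is unknown, any AE that could have worsened in the treatment window is taken as treatment-emergent. The test is Most Extreme Grade above Initial Grade. The worked example uses the first parent-study dose, although the definition in the same section uses the first rollover dose.

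Appendix 2 gives an algorithm for treatment emergence based on start and stop dates. Its rows for known start dates include: "If start date < study drug start date, then not TEAE". No row looks at grade. A note below the table defines study drug start as the first dose in the parent study.

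**The concern.** Every patient enters while receiving IMCgp100, so an AE may have begun, peaked and partly resolved before the first rollover dose and still be open at entry. Deciding whether it worsened on rollover needs the grade at rollover entry and the highest grade afterwards. The fields described in SAP 15.1 supply neither. SAP 6.2 declines change-from-baseline analyses because patients were already on drug, but AE worsening has no comparable safeguard.

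At stake are the primary AE tables: TEAEs by system organ class and preferred term, for all grades and for Grade 3 or above, repeated for related TEAEs. A peak reached in the parent study could appear as a severe rollover event, or a real deterioration on rollover could go uncounted. The result also depends on whether the programmer follows the text of 15.1 or the rows of Appendix 2.

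**Working it through.** There is no planned figure to reproduce: "No formal sample sizing will apply to this study" (Protocol 9.9) and "There will be no formal statistical hypotheses testing" (SAP 6.5). The check is therefore logical. It lists every possible course of a carried-over AE and applies each rule.

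**Inputs.** Take an AE still ongoing at the first rollover dose, with grades 1 to 4. Let *i* = grade at onset, *p* = peak before the first rollover dose, *e* = grade at rollover entry, and *r* = peak from the first rollover dose onward. Then *p* ≥ max(*i*, *e*) and *r* ≥ *e*. True worsening on rollover is *r* > *e*. One assumption is needed: Initial Grade = *i* and Most Extreme Grade = max(*p*, *r*), as the single-record rule and the parent-study start date imply.

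**Number of paths.** For a given *e*, the number of (*i*, *p*) pairs is the sum over *i* of 5 − max(*i*, *e*), which is 10, 9, 7 and 4 for *e* = 1, 2, 3, 4. The choices of *r* number 5 − *e*.
- All paths: 10×4 + 9×3 + 7×2 + 4×1 = 85.
- Not worsening (*r* = *e*): 10 + 9 + 7 + 4 = 30.
- Worsening: 85 − 30 = 55.

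**SAP 15.1 (max(*p*, *r*) > *i*).**
- A non-worsening path escapes being counted only if *p* = *i* and *e* ≤ *i*, which gives 1 + 2 + 3 + 4 = 10 paths. So 30 − 10 = 20 are counted.
- A worsening path is missed if *p* = *i* and *e* < *r* ≤ *i*. For *i* = 1 to 4 this gives 0 + 1 + 3 + 6 = 10 paths.
- A Grade 3 or higher TEAE is tabulated although the rollover peak is below 3 when *p* ≥ 3, *p* > *i* and *r* ≤ 2. There are 5 (*i*, *p*) pairs and 3 (*e*, *r*) pairs: 5×3 = 15 paths.

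**Appendix 2 (dates only).** All paths with the same start date get the same answer.

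| Rule | Non-worsening paths counted (of 30) | Worsening paths missed (of 55) |
|---|---|---|
| SAP 15.1 | 20 | 10 |
| Appendix 2 as written, onset on or after first parent dose | 30 | 0 |
| Appendix 2 as written, onset before first parent dose | 0 | 55 |
| Appendix 2 with only the anchor moved to first rollover dose | 0 | 55 |

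**Four illustrative records**, all with onset on parent-study drug:

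| Onset / parent peak / entry / rollover peak | Worsened on rollover? | SAP 15.1 | Appendix 2 as written | Appendix 2, rollover anchor |
|---|---|---|---|---|
| 1 / 3 / 1 / 1 | No | TEAE, Grade 3 | TEAE | Not TEAE |
| 3 / 3 / 1 / 3 | Yes | Not TEAE | TEAE | Not TEAE |
| 1 / 1 / 1 / 3 | Yes | TEAE, Grade 3 | TEAE | Not TEAE |
| 2 / 2 / 2 / 2 | No | Not TEAE | TEAE | Not TEAE |

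**Direct conflict.** The example in 15.1 is an AE that began before the first parent dose, continued past it and rose above its initial grade. That section makes it a TEAE; Appendix 2, as its note is written, makes it not a TEAE.

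**The case against.** Four points on the other side carry weight.

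- **SAP 15.1 arguably governs.** SAP 15 sends the reader to 15.1 for the definition of treatment emergence, and 15.1 cites Appendix 2 only for partial dates, as the appendix title suggests. This stands as a reading of the hierarchy. But the appendix has rows where both dates are known and is headed as the algorithm for treatment emergence, so it could be programmed as such.
- **The over-count in 15.1 is a declared worst case.** The SAP says the date of grade change is not collected and errs towards counting, which is defensible in a descriptive safety study. The listing also shows TEAEs and non-TEAEs as recorded. However, the convention departs from Protocol 9.6.1.1, is not among the changes in SAP 3.3, and is not reliably conservative, since it misses 10 worsening paths.
- **Initial Grade is undefined for carried-over AEs.** If eCRF instructions made it the grade at rollover entry, and Most Extreme Grade the peak since entry, the 15.1 part would disappear. Protocol 8.1.1 also counts worsening of a pre-existing condition as an AE. Nothing supplied settles this, and the single-record rule points towards the onset grade.
- **The any-AE patient count may barely move**, because a patient with any other TEAE is already in it. This stands.

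A reader might also infer that Appendix 2, as written, drops an AE that began on parent drug and worsened on rollover. It does not: its anchor is the first parent dose, so that AE is counted. Such AEs are lost only if the anchor is moved to the first rollover dose without adding a worsening branch. As written, the appendix loses worsening only for AEs that began before the first parent dose.

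**Conclusion.** The point holds as an inconsistency that should be fixed together with the Appendix 2 anchor date. For AEs ongoing at rollover entry, the two rules in the SAP conflict, and neither reliably separates AEs that worsened on rollover treatment from those that did not. Under 15.1 errors run both ways (20 of 30 and 10 of 55 possible paths), provided Initial Grade is the onset grade. The Appendix 2 finding does not need that assumption, because the algorithm ignores grade.

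The path counts show which errors are possible, not how often they occur. The documents give no patient numbers, AE rates or number of AEs open at entry, so the effect on the primary endpoint is unknown. A reader might infer that the primary count is materially inflated, or that ongoing AEs at entry are the usual case; the documents support neither. Rows by system organ class and preferred term, and those at Grade 3 or above, are more exposed than the any-AE patient count.

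**What to change.** 1. In the Appendix 2 AE algorithm, set study drug start to the first rollover dose, as in the 15.1 definition. In the same edit add a branch: if the AE began before the first rollover dose, and its maximum grade from that dose to 90 days after the last dose exceeds its grade before dosing on Rollover Cycle 1 Day 1, it is a TEAE, tabulated at that on-rollover maximum; otherwise it is not. The branch should also cover partial start dates that can only fall before the first rollover dose.
2. For each AE flagged as ongoing at study start, obtain two items before database lock, by one site query or from the parent database: the pre-dose grade on Rollover Cycle 1 Day 1 and the maximum grade after it. The entry grade alone is not enough, because Most Extreme Grade may still come from the parent study.
3. Keep the worst-case rule of 15.1 only where these grades cannot be recovered. Correct its example to the first rollover dose, and footnote how many AEs were classified that way.

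With both grades available, all 85 paths are classified correctly by construction (55 TEAE, 30 not). The cost is two data items per carried-over AE, one query each at most, and one program branch. Some grades may be unrecoverable; those AEs stay on the worst-case rule.

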15.1.1. All TEAEs

Incidence of TEAEs by subject count, in addition to number of total TEAEs, will be presented by System Organ Class (SOC) and Preferred Term and also broken down further by maximum severity of the NCI CTCAE grade (Grade ≥3).

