**Table 4-1 Objectives and Related Endpoints**

Objective(s)	Endpoint(s)
Primary	
To determine the number of patients with adverse events associated with IMCgp100 treatment	Incidence of adverse events
Secondary	
To characterize the long-term safety (> 1 year dosing) and tolerability of IMCgp100	Tolerability: Dose interruptions, reductions, and dose intensity of IMCgp100

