## **9.5 Primary Analysis**

### **9.5.1 Variables**

The primary variable is the incidence of AEs.

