2.2. Secondary Objectives

- To characterize the long-term safety (> 1 year dosing) and tolerability profile associated with treatment with IMCgp100
- To evaluate the incidence of anti-IMCgp100 antibody formation following multiple infusions of IMCgp100
- To estimate the overall survival (OS) in patients treated with IMCgp100.

3. Study Design

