7.5. Examination of Subgroups

No subgroups will be defined for this study.

8. Output Presentations

[APPENDIX 1](#) shows conventions for presentation of data in outputs.

The template shells provided with this SAP describe the presentations for this study and therefore the format and content of the summary tables, figures, and listings to be provided by

IQVIA Biostatistics.

9. Disposition and Withdrawals

All patients who provide informed consent will be accounted for in this study. Any subjects who signed the informed consent, but never started the study treatment for any reason will be regarded as screen failures. For these patients, the eCRF data collected will not be included in summary analyses but will be reported in the CSR as part of the listings.

Patient disposition and discontinuation/withdrawals will be presented for the All Patients Enrolled (ENR) set. Important protocol violations will be listed for the Full Analysis Set (FAS).

10. Demographic and other Baseline Characteristics

Demographic data and other baseline characteristics will be presented for the FAS.

The following demographic and other baseline characteristics will be listed for this study:

1. Demography
 - Age (years)
 - Sex
 - Is the patient of child bearing potential? (females only)
 - Race
 - Ethnicity
 - Country
 - Weight (kg)
 - Height (cm)
 - BMI (kg/m²)
2. Disease data
 - Diagnosis and extent of cancer (disease at baseline)
 - Prior anti-cancer therapy

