13.1. Study Drug Exposure Derivations

A cycle is defined as 28 days = 4 weeks, and at least 1 dose administration visit per cycle for each of the treatment regimen for IMCgp100 (doses are given every week).

The following will be derived:

- *Number of cycles started* = total number of cycles of study drug received (including partial cycles), during the rollover study
- *Number of cycles completed* = total number of complete cycles of study drug received without any interruption, during the rollover study
- *Total planned dose* = sum of the total dose levels that a patient planned to receive during the rollover study, up to the date of last study drug administration
- *Duration of treatment (days)* = (date of last study drug administration – date of first study drug administration in the rollover study + 1). Note that this calculation does not include any post dose rest period. *Duration of treatment from first parent study dose (days)* = (date of last study drug administration – date of first parent study dose of IMCgp100 + 1). Note that this calculation does not include any post dose rest period
- *Duration of interruption (days)* = (start date of next study drug administration following interruption - date of visit in which interruption started). Note that this is calculated for each interruption a given patient has and is only calculated where study drug administration restarts following interruption.
 - “Date of visit in which interruption started” = ‘date of visit’ from the *Date of Visit* eCRF pages, where the visit may also be a visit classified as “not done”. If it is clear that an interruption to dosing has occurred, but no *Date of Visit* eCRF page nor *Administration of Study Drug* eCRF page is entered at least 14 days (i.e. at least 7 days ± 7 day visit window) following the previous dosing visit, where dosing would have been expected, then the date of the *expected* next dose following last administered dose, may be used instead (=previous ‘start date of study drug administration’ + 14 days). See the definition of a *dose interruption* below.
 - If a patient does not have a “start date of *next* study drug administration following interruption” then a dose interruption is not counted because either:
 - The Date of study drug discontinuation from the *End of Treatment* page of the eCRF is filled out, in which case the study drug was discontinued rather than interrupted, or

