15.1.1.1. NATIONAL CANCER INSTITUTE COMMON TERMINOLOGY CRITERIA FOR ADVERSE EVENTS (CTCAE) GRADE

Severity is based on NCI CTCAE v.4.03 grades and classed as mild, moderate, severe, life threatening, or death related to AE (increasing severity), as represented by Grades 1-5, respectively. TEAEs starting after the first dose of study drug with a missing severity will be classified as ‘missing’. If a patient reports the same AE more than once within that SOC/PT, the AE with the worst-case severity will be used in the corresponding severity summaries. In determining maximum severity, response values will be ranked in order from minimum severity to maximum severity as Missing, Grade 1, Grade 2, Grade 3, Grade 4, and Grade 5 (as values: ‘missing’, ‘mild’, ‘moderate’, ‘severe’, ‘life threatening’, and ‘death related to AE’).

A summary table will present TEAEs, showing number of subjects (%) for all grades and grades ≥ 3 for each SOC/PT. This summary table will also be repeated for TEAEs related to IMCgp100.

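### No planned adverse-event summary covers the safety half of the secondary objective on more than 1 year of dosing

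*SAP*

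**What the plan says.** Protocol 4.2 and SAP 2.2 state the secondary objective as "To characterize the long-term safety (> 1 year dosing) and tolerability profile associated with treatment with IMCgp100". Protocol Table 4-1 gives it one endpoint: "Tolerability: Dose interruptions, reductions, and dose intensity of IMCgp100". Adverse events are the subject of the primary objective, which asks how many patients have them; Protocol 9.5.1 says "The primary variable is the incidence of AEs".

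SAP 15.1 defines treatment-emergent adverse events (TEAEs) this way: "AEs that started or worsened in severity from the date of first dose of the rollover study (regardless of time) up until 90 days after"; this window closes 90 days past the final rollover dose. SAP 15.1.1 plans the tabulation: "Incidence of TEAEs by subject count, in addition to number of total TEAEs, will be presented by System Organ Class (SOC) and Preferred Term". SAP 15.1.1.1 adds: "A summary table will present TEAEs, showing number of subjects (%) for all grades and grades ≥ 3 for each SOC/PT", repeated for related events. Serious events are listed (SAP 15.1.3).

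No section of either document plans a TEAE rate per unit of person-time, an interval for a TEAE proportion, or a breakdown of TEAEs by time on drug. SAP 7.5 says "No subgroups will be defined for this study". Confidence intervals appear only as a formatting convention in SAP Appendix 1. Exposure is summarised separately under SAP 13, including duration from the first parent-study dose, derived as "date of last study drug administration – date of first parent study dose of IMCgp100 + 1".

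**The concern.** The objective names both safety and tolerability. Tolerability has endpoints and, in SAP 13, summaries of interruptions and dose intensity. Safety beyond 1 year has neither an endpoint in Table 4-1 nor a planned adverse-event display.

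The general TEAE table does not fill the gap, for two reasons. Its window opens at the first rollover dose, not at the end of the first year on drug, so it can pool both periods. Its length also differs by patient, because dosing continues until individual loss of benefit (Protocol 3.3). A crude proportion rises with follow-up even if the risk per unit time is constant. From that table alone a reader cannot tell whether late events are frequent because risk persists or because patients stayed long. In an unsized study, few or no events of a given type could also be read as more reassuring than the data allow.

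**Working it through.** The documents state no sample size, event rate or precision, so there is no planned figure to reproduce. The steps below use the documents' rules; assumed inputs are marked.

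**1. Does the rollover TEAE table isolate dosing beyond 1 year?** Protocol 2.1 asks for at least 4 weeks (28 days) of prior dosing. A patient entering at that minimum contributes up to 365 − 28 = 337 days of rollover time, about 11 months, before reaching 1 year. A patient who enters after more than a year contributes none. Both are counted in the same table.

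**2. How much does crude incidence depend on time on drug?** Assume a constant rate λ of first events per patient-year. A patient with m months on rollover drug is at risk for m/12 + 90/365.25 years, the second term being the 90-day tail in SAP 15.1. Expected crude incidence is 1 − exp[−λ(m/12 + 90/365.25)].

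- λ = 0.5, m = 3: 1 − exp[−0.5 × (0.25 + 0.2464)] = 22.0%.
- λ = 0.5, m = 24: 1 − exp[−0.5 × (2 + 0.2464)] = 67.5%.

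| Assumed λ per year | 3 months | 6 months | 12 months | 24 months |
|---|---|---|---|---|
| 0.25 | 11.7% | 17.0% | 26.8% | 43.0% |
| 0.5 | 22.0% | 31.1% | 46.4% | 67.5% |
| 1.0 | 39.1% | 52.6% | 71.2% | 89.4% |

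The tail must be included. Without it, λ = 0.5 gives 11.8% and 63.2%, a ratio of about 5 (63.2/11.8). With it the ratio is about 3 (67.5/22.0).

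**3. Can one crude display hide different rates?** Assume 2 of 10 patients have a first event, shown as 20% (exact 95% CI 2.5% to 55.6%). Exact Poisson limits for 2 events, divided by person-time, give:

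- over 5 patient-years: 40.0 per 100 patient-years (4.8 to 144.5);
- over 20 patient-years: 10.0 per 100 patient-years (1.2 to 36.1).

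The point estimates differ fourfold and the planned percentage is identical. The intervals overlap widely, so the addition makes the data interpretable, not precise.

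**4. What does zero events mean?** The exact two-sided 95% upper limit is 1 − 0.025^(1/N): 52.2% at N = 5, 30.8% at N = 10, 16.8% at N = 20 and 7.1% at N = 50 (N assumed).

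**5. Is the risk window settled?** No. SAP 15.1 defines treatment emergence from the first rollover dose. The note under the TEAE algorithm in SAP Appendix 2 sets the drug start date to the first parent-study dose, and the worked example on worsening in SAP 15.1 also uses the parent date. The choice fixes both the numerator and the person-time.

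**The case against.** The best case for the plan is that it does what it was set up to do. The primary objective is a number of patients, and a patient count supplies it. Table 4-1 assigns the long-term objective to tolerability, which SAP 13 summarises together with duration from the first parent dose. The study is a single-arm access study with no hypothesis tests (SAP 6.5) and no sample sizing (Protocol 9.9), and no section plans a comparison with parent-study incidence. Total TEAEs are planned as well as patients, so with the duration summary a rough overall event rate can be formed. Study Day is shown for events (SAP 6.1), so late events can be found in the listings.

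Most of this stands, and it rules out stronger readings. A reader might infer that the TEAE analysis is a bare patient count, that it makes the primary result wrong, or that the study cannot address long-term safety at all. The documents support none of these.

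The narrower gap remains. Total events over total duration give no first-event rate and no split at 1 year. Study Day runs from the first rollover dose, so each listed event would have to be re-dated by hand to the parent-study clock. Descriptive status is no reason to omit rates or intervals, since both are descriptive. Nor does SAP 7.5 stand in the way: dividing a patient's own follow-up time does not define a patient subgroup.

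One limit applies. SAP 15.1 refers to table templates that are not among the documents, so a further display there cannot be excluded.

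**Conclusion.** The point holds as a gap in coverage: the safety half of one secondary objective has no planned adverse-event summary. It is an inexpensive improvement, not an error in the primary analysis. The dependence of crude incidence on time on drug follows from open-ended treatment and the TEAE window. Its size rests on assumed inputs: a constant rate of 0.25 to 1.0 first events per patient-year, 3 to 24 months on drug, and N of 5 to 50. The documents give neither the spread of follow-up nor the number of patients, so nothing here shows that either is extreme.

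A reader might also expect a split at 1 year to show whether the drug's risk changes with time. It would not. Patients roll over because they tolerated treatment and were judged to benefit (Protocol 2.1 and 5.2), and early rollover time comes only from those who entered within their first year.

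**What to change.** Keep the existing TEAE tables.

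1. Reconcile the TEAE start date between the definition in SAP 15.1, its worked example and the Appendix 2 note.
2. Add to SAP 15.1.1 one table, labelled descriptive, for any, related, Grade ≥3 and serious TEAEs, giving:
   - (a) the proportion of patients with an exact 95% CI;
   - (b) first events per patient-year with an exact 95% CI, overall and by person-time ≤365 and >365 days from the first parent-study dose.
3. Use rollover events and rollover time only. End time at risk at the earliest of the first event within that period, last dose + 90 days, death or last contact.
4. State a convention for events that are treatment-emergent only through worsening. The eCRF records initial and most extreme grade but no date of change (SAP 15.1). Count these events in (a), and assign them to a period in (b) by the stated rule.
5. Add to Protocol Table 4-1, or to the SAP's list of changes from the protocol, that this table serves the safety part of the long-term objective.

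The cost is modest. The first parent-dose date is already needed for SAP 13.1 and for overall survival, but time to first event, the 90-day end of risk and the split person-time are new derivations, and serious events would be tabulated as well as listed. Intervals will be wide. The ≤365-day stratum may be sparse and is selected for tolerance, so a footnote should warn against reading the split as a causal comparison.
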